5.8. Analysis of Safety Data

Safety and tolerability will be descriptively summarized, including AEs, clinical laboratory variables, physical exam, and vital signs for the SAF. The summary of safety results will be presented for the treatment groups of combined REGN2222 dose arms with the intent to maximize efforts to detect potential safety signals. The individual REGN2222 dose arms will also be presented with the intent to support the combined regimens. No formal inferential testing will be performed. Summaries will be descriptive in nature.

All safety analyses will be performed, unless otherwise specified, using the following common rules:

- The baseline value is defined as the last available value obtained up to the date and time of the first dose of study drug, unless otherwise specified.
- For clinical laboratory, physical exam, and vital signs variables, all measurements, scheduled or unscheduled, will be assigned to analysis windows defined in Appendix 11.3 in order to provide an assessment for Visit 3 to Visit 7 time points.
- For continuous safety parameters including central laboratory measurements and vital sign scores, descriptive statistics will be used to summarize results and change from baseline values by visit.
- A treatment-emergent Potential Clinically Significant abnormal value (PCSV) is a laboratory value or vital sign that was: normal at baseline but abnormal after treatment with study drug during the TEAE period, or: abnormal at baseline and worsened after treatment with study drug during the TEAE period. Thresholds for treatment-emergent PCSV in laboratory variables and vital signs are defined in Appendix 11.4. Treatment-emergent PCSV criteria will determine which subjects had at least 1 treatment-emergent PCSV, taking into account all assessments including unscheduled assessments. Subjects who had post-baseline PCSV during the TEAE period but missing baseline value will be regarded as having treatment-emergent PCSV. There are no universally accepted normal ranges for preterm infants. The ranges used to determine PCSV criteria are associated with full-term infants (except

for bilirubin) and consequently, the TEPCSV results are to be interpreted with caution.

The summary of safety results will be presented by treatment group (REGN2222 1 dose, REGN2222 2 doses, REGN2222 combined, and placebo).

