5.8.4. Analysis of Vital Signs

All collected vital sign measures (pulse rate, respiratory rate, sitting blood pressures, and temperature) will be explored through summaries of both the actual measurements (at both baseline and post-baseline) and the change from baseline measurements at each post-baseline scheduled visit. Descriptive statistics include number of subjects, mean, median, standard deviation, minimum, Q1, Q3, and maximum values for each treatment group. In addition, body weight will be summarized in the same fashion.

The obtainment of blood pressure in infants, without cause or suspicion of underlying abnormalities is not routinely done in the outpatient pediatric setting. Specialized equipment, not routinely present in pediatric physician offices, is required. As a result of the issues surrounding the accurate obtainment of blood pressures in the study's infant population, the study protocol was revised to allow investigators to record that blood pressures are not able to be obtained. In many instances blood pressure results are not available, and in instances where results have been obtained, the accuracy of the recordings can be questioned. As a result, no shift table or treatment-emergent PCSV analyses will be performed on blood pressure measurements.

The protocol allows for the measurement of subject temperature using different modalities, eg, temporal, axillary, rectal and tympanic. Temperatures measured using different modalities are not equivalent and conversions are necessary to allow comparison. Furthermore, as the child ages throughout their time participating in the study, elevations in temperature that would be of concern change. Therefore due to the complexities to standardize reporting of temperatures and to accommodate changes reflecting the age of the child over time, no shift table or treatment-emergent PCSV analyses will be performed on temperature measurements.

Only the number (and percentage) of subjects with pulse rate and respiratory rate values meeting the treatment-emergent PCSV criteria at least once during the TEAE period will be summarized. Subject listings of vital sign measurements that meet treatment-emergent PCSV criteria will be provided.

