11.4. Criteria for Treatment-Emergent Potentially Clinically Significant Values (PCSV)

| Parameter | PCSV | Comments |
|--------------------------------------------------------------------------------------------------------------------------------------------------------------------------------------------------------------------------------------------------------------------------------------------------------------------------|----------------------------------------------------------------------------------------------------------------------------------------------------------------------------------------------------------------------------------------------------------------------------------------------------------------------------------------------------------------------------------------------------------------------------------------------------------------------------------------------------------------------------------------------------------------------------------------------|--------------------------------------------|
| Clinical chemistry | | |
| PCSV based on criteria for infants born at term, except for total bilirubin where specific criteria are available for pre-term infants, considering Grade 3 Severe and above events as per the Division of AIDS (DAIDS) Table for Grading the Severity of Adult and Pediatric Adverse Events Version 2.0 November 2014). | | |
| ALT, high | ≥ 5 ULN and baseline < 5 ULN | |
| Albumin, low | < 20 g/L and baseline ≥ 20 g/L | |
| AST, high | ≥ 5 ULN and baseline < 5 ULN | |
| Alkaline Phosphatase, high | ≥ 5 ULN and baseline < 5 ULN | |
| Calcium, high | Meeting the following PCSV criteria for at least one post-baseline measurement and no PCSV at baseline ≥ 3.13 mmol/L for ≥ 7 days of age ≥ 3.23 mmol/L for < 7 days of age | |
| Calcium, low | Meeting the following PCSV criteria for at least one post-baseline measurement and no PCSV at baseline < 1.75 mmol/L for ≥ 7 days of age < 1.50 mmol/L for < 7 days of age | |
| Carbon Dioxide, low | < 11.0 mmol/L and baseline ≥ 11.0 mmol/L | |
| Creatinine, high | > 1.8 ULN and baseline ≤ 1.8 ULN, or Increase of 1.5 x above baseline | |

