| Hemoglobin, low | Meeting the following PCSV criteria for at least one post-baseline measurement and no PCSV at baseline < 6.19 mmol/L (100 g/L) for ≤ 7 days of age < 5.57 mmol/L (90 g/L) for 8 to ≤ 21 days of age < 4.94 mmol/L (80 g/L) for 22 to 35 days of age < 4.32 mmol/L (70 g/L) for 36 to 56 days of age < 5.25 mmol/L (85 g/L) for ≥ 57 days of age | |
| Platelets, decreased | $< 50.000 \times 10^9$ cells/L and baseline $\geq 50.000 \times 10^9$ cells/L | |
| Vital signs | | |
| PCSV based on normal ranges in http://health.ny.gov/professionals/ems/pdf/assmttools.pdf | | |
| Respiratory Rate | < 30 breaths per minute and ≥ 30 breaths per minute at baseline > 60 breaths per minute and ≤ 60 breaths per minute at baseline | |
| Pulse Rate | < 100 beats per minute and ≥ 100 beats per minute at baseline > 160 beats per minute and ≤ 160 beats per minute at baseline | |

11.5. Hypersensitivity PTs of interest per Carbonell-Estrany X et al.

| Non-Specific PTs | Specific PTs |
|-------------------------|---------------------------|
| Erythema | Anaphylactoid reaction |
| Flushing | Angioedema |
| Pruritus | Dermatitis allergic |
| Rash | Drug eruption |
| Rash erythematous | Drug hypersensitivity |
| Rash macular | Oedema |
| Rash maculo-papular | Erythema annulare |
| Rash pruritic | Erythema marginatum |
| | Erythema multiforme |
| | Eye swelling |
| | Eyelid oedema Face oedema |
| | Hypersensitivity |
| | Injection site erythema |
| | Laryngeal oedema |
| | Lip swelling |
| | Periorbital oedema |
| | Rash generalised |
| | Swelling |
| | Swelling face |
| | Tracheal oedema |
| | Urticaria |
| | Urticariapapular |

Note: The following terms listed in Carbonell-Estrany's manuscript are LLTs that code into PTs as follows:

LLT: Angioneurotic oedema codes to PT: Angioedema

LLT: Exanthema codes to PT: Rash

LLT: Urticaria generalised codes to PT: Urticaria.

11.6. Hypersensitivity PTs of interest per Feltes TF et al.

| Non-Specific PTs | Specific PTs |
|----------------------|------------------------|
| Erythema | Allergic oedema |
| Fixed Drug Eruption | Anaphylactoid reaction |
| Generalised oedema | Angioedema |
| Pruritus | Bronchial oedema |
| Pruritus generalised | Circumoral oedema |
| Rash | Dermatitis allergic |
| Rash erythematous | Drug eruption |
| Rash macular | Drug hypersensitivity |
| Rash maculo-papular | Erythema annulare |
| Rash papular | Erythema marginatum |
| Rash pruritic | Erythema multiforme |
| | Eye oedema |
| | Eye swelling |

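### The SAP Appendix 11.4 pulse and respiratory-rate rules cannot count an infant who starts beyond the limit and gets worse, although SAP 5.8 says such an infant is a treatment-emergent PCSV

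*SAP*

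**What the plan says.** SAP 5.8 (Analysis of Safety Data) defines a treatment-emergent PCSV for laboratory values and vital signs by either of two routes:

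- Route 1: "normal at baseline but abnormal after treatment with study drug during the TEAE period"
- Route 2: "abnormal at baseline and worsened after treatment with study drug during the TEAE period"

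It then says: "Thresholds for treatment-emergent PCSV in laboratory variables and vital signs are defined in Appendix 11.4". All assessments, including unscheduled ones, feed the count. An infant with a post-baseline PCSV and a missing baseline is counted as treatment-emergent.

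SAP Appendix 11.4 describes its vital-sign limits as taken from a table of normal ranges. The respiratory-rate rules are "< 30 breaths per minute and ≥ 30 breaths per minute at baseline" and "> 60 breaths per minute and ≤ 60 breaths per minute at baseline". The pulse rule on the high side is "> 160 beats per minute and ≤ 160 beats per minute at baseline", with a matching low rule at 100.

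SAP 5.8.4 drops PCSV and shift-table analyses for blood pressure and temperature. What remains is: "Only the number (and percentage) of subjects with pulse rate and respiratory rate values meeting the treatment-emergent PCSV criteria at least once".

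For creatinine, Appendix 11.4 reads "> 1.8 ULN and baseline ≤ 1.8 ULN, or Increase of 1.5 x above baseline".

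**The concern.** In 11.4 the limit that makes a pulse or respiratory rate abnormal is also the limit that the baseline must not have crossed. Route 2 of 5.8 needs an abnormal baseline, and 11.4 rules out every such baseline for the same direction. An infant with pulse 165 before the first dose and 210 one hour after it meets the definition in 5.8 but not the criterion in 11.4.

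At stake is what the only vital-sign PCSV table, and the listing built from it, can show. SAP 5.8 presents the combined REGN2222 arms in order to maximise detection of safety signals. A rule that leaves out documented worsening, yet counts an infant whose baseline is unknown, does not serve that aim. A programmer also has two texts that disagree, and nothing else in the SAP reconciles them.

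**Working it through.** The documents state no figure on this point, so there is none to reproduce. The check applies the 11.4 rules as written and compares the result with 5.8.

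**Inputs.** Limits from SAP 11.4: respiratory rate low 30, high 60; pulse low 100, high 160. Rule: flag if (post < low and baseline ≥ low) or (post > high and baseline ≤ high). The enumeration covers every whole-number baseline/post pair for respiratory rate 5–120 and pulse 40–260. These grids are my choice; the zeros below do not depend on them.

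**Same-direction worsening from an abnormal baseline** (baseline > high and post > baseline, or baseline < low and post < baseline):

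- Respiratory rate: (0 + 1 + … + 59) + (0 + 1 + … + 24) = 1,770 + 300 = 2,070 pairs, 0 flagged. Example: 65 to 80 is not flagged.
- Pulse: (0 + 1 + … + 99) + (0 + 1 + … + 59) = 4,950 + 1,770 = 6,720 pairs, 0 flagged. Example: 170 to 200 is not flagged.

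**Normal to abnormal:**

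- Respiratory rate: 31 baselines × (25 + 60) abnormal values = 2,635 pairs, all flagged.
- Pulse: 61 × (60 + 100) = 9,760 pairs, all flagged.

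**Swing to the opposite abnormality:** 3,000 of 3,000 (respiratory rate) and 12,000 of 12,000 (pulse) are flagged. That is a new abnormality, not a worsening of the baseline one.

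The pair counts show how the rule behaves. They are not frequencies in infants.

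**Does the reading of abnormal in 5.8 matter?** If it means outside the normal range, the 11.4 vital-sign limit is that range, so route 2 is empty. If it means meeting 11.4, the baseline condition empties route 2 again. Laboratory rows with a cut-off well above the upper limit of normal (ULN) differ on the first reading: ALT from 2 to 6 times ULN is abnormal then worse, and is counted. ALT from 6 to 10 times ULN is not.

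**Do other outputs fill the gap?** SAP 4.7.4 schedules vital signs before injection and 1 hour after. The analysis windows in SAP 11.3 begin at Day 15, so the Day 1 post-injection reading falls in none of them. Under SAP 6.4, when times are available the first value of a day is kept, so on Day 57 the pre-dose reading is used. No shift table is planned for pulse or respiratory rate. The PCSV count is therefore the planned vital-sign summary that reaches the Day 1 post-injection reading.

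**Creatinine.** The second limb can be read two ways. As 1.5 times baseline, 0.2 mg/dL is flagged at 0.2 × 1.5 = 0.3 mg/dL. As a rise of 1.5 times baseline, it is flagged at 0.2 × 2.5 = 0.5 mg/dL. The two readings would give different tables.

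**The case against.** The strongest reply is that the operative rule is not in doubt. SAP 5.8 sends the reader to 11.4 for thresholds and says the criteria there decide who is counted, so a programmer would apply 11.4. Counting only new crossings is a defensible meaning of treatment-emergent. The arms share one rule, nothing is tested, and 5.8 already urges caution. Change-from-baseline summaries include the maximum, and protocol 7.2.6 provides for some abnormal vital signs to be reported as adverse events.

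Much of this stands, and it limits how serious the point is. It does not remove the contradiction: 5.8 explicitly adopts the broader meaning, its caution concerns full-term reference ranges, and the by-visit summaries miss the Day 1 post-injection value. Adverse-event reporting is a partial backstop, since it depends on symptoms, further testing or intervention, discontinuation or similar conditions.

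Two stronger readings are tempting and are not supported.

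- A reader might infer that many infants are missed. The documents give no pulse or respiratory-rate distribution. A simulation assuming mean pulse 135–145, between-infant SD 8–12, within-infant SD 10–15 and seven later readings puts 0.7% to 14% of infants above 160 at baseline and later higher. That range is mostly assumption, contains no drug effect and counts any rise at all. Even in its extreme corner, only 3.0% rise by more than 20 beats per minute and under 0.1% by 45. The SAP does not state the PCSV denominator either.
- A reader might infer that the creatinine limb contradicts 5.8 because it can flag a value still within normal, and so needs a ULN condition. That holds only if normal in 5.8 means within ULN. On that reading most laboratory rows would conflict too: ALT rising from within ULN to 2 times ULN is normal then abnormal, yet is not counted. SAP 11.4 attributes its chemistry criteria to a published grading scale whose general chemistry pages are not reproduced in the protocol, so the origin of the limb cannot be checked. The limb is also the one laboratory criterion that can register worsening beyond its own fixed cut-off. A ULN condition could reduce sensitivity where the SAP says no preterm range is accepted.

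**Conclusion.** The point holds for pulse and respiratory rate. Route 2 of the SAP 5.8 definition cannot operate under the 11.4 rules for worsening in the same direction, on either reading of abnormal. This follows from the text alone and rests on no assumed data.

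The consequence is confined to a descriptive safety count and its listing. Efficacy, type I error and power are unaffected, and the number of infants concerned cannot be derived from the documents. For creatinine, what remains is an ambiguous multiple and a baseline-relative limb that 5.8 does not mention. It is worth settling before programming, as a modest correction.

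**What to change.** Reconcile SAP 11.4 with 5.8 before the tables are programmed.

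- **Pulse and respiratory rate:** keep the existing rows for new crossings. Add a separate descriptive row, with a listing, for infants beyond the limit at baseline whose post-baseline value is further beyond it in the same direction. Use all assessments, including the post-injection readings, and present it by treatment group.
- **Creatinine:** state whether the second limb means 1.5 or 2.5 times the baseline value, and note in 5.8 that this limb is relative to baseline. Do not add a ULN requirement.

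The cost is a few lines of SAP text, one table row per sign and one listing. The small downside is that the new row also picks up random worsening. Keeping it separate leaves the existing count intact, and the placebo arm gives the background rate against which to read it.

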5.8.1. Adverse Events

The verbatim text, the PT, and the primary SOC will be listed in subject listings. Summaries that include frequencies and proportions of subjects reporting AEs will include the PTs and the SOCs as appropriate.

The focus of adverse event reporting in the clinical study report will be on TEAEs. Pre-treatment and post-treatment AEs will be provided separately.

If an AE date/time of onset (occurrence, worsening, or becoming serious) is incomplete, an imputation algorithm will be used to classify the AE as pre-treatment, treatment-emergent, or post-treatment. The algorithm for imputing date/time of onset will be conservative and will classify an AE as treatment-emergent unless there is definitive information to determine pre-treatment status. For details on handling missing data and partial dates, see Section 6.3.

Summaries of all TEAEs in each treatment group will include:

- Overview of TEAEs, summarizing number and percentage of subjects with any
 - TEAEs.
 - Serious TEAEs.
 - TEAEs leading to death.
 - TEAEs leading to permanent treatment discontinuation.
 - TEAEs with severity of 3/4/5/Severe/Life-Threatening/Fatal (if multiple occurrences of an event for a subject, then worst severity is counted).
 - TEAEs that occurred within 2 days after either the first dose or the second dose (ie, post dose TEAE start date - dosing date \leq 2).
- All TEAEs by SOC and PT.
- All TEAEs by SOC, PT, and severity.
- All TEAEs by SOC, PT, and relationship (related, not related) to study drug.
- All TEAEs by SOC, PT, and relationship (related, not related) to injection procedure.
- TEAEs reported by \geq 5% of subjects in any treatment group by PT ordered by decreasing subject frequency in the combined REGN2222 group.
- TEAEs reported by \geq 1% of subjects in any treatment group by PT ordered by decreasing subject frequency in the combined REGN2222 group.
- Study drug-related TEAEs by SOC and PT.
- Study drug-related TEAEs by SOC, PT, and severity.
- Injection procedure-related TEAEs by SOC and PT.
- Injection procedure-related TEAEs by SOC, PT, and severity.

- Serious adverse events: All, study drug-related, and injection procedure-related TEAEs by SOC and PT.
- Death: All, study drug-related, and injection procedure-related TEAEs by SOC and PT. TEAEs leading to death are TEAEs that led to death regardless of timing of death in relation to study drug injection (ie, death occurring in the TEAE period or during the post-treatment period)
- Discontinuation of study drug: All, study drug-related, and injection procedure-related TEAEs by SOC and PT.
- TEAEs with severity of 3/4/5/Severe/Life-Threatening/Fatal: All, study drug-related, and injection procedure-related TEAEs by SOC and PT.
- Non-serious study drug-related or injection procedure-related TEAEs by SOC and PT.
- TEAEs according to time of occurrence in relation to dosing:
 - TEAEs that occurred after the first dose and before the second dose: All, study drug-related, and injection procedure-related TEAEs by SOC and PT. For subjects who did not receive the second dose, only TEAEs that occurred up to Day 57 (Day 1 being the day when the first dose was administered) will be included.
 - TEAEs that occurred after the second dose in subjects who received the second dose: All, study drug-related, and injection procedure-related TEAEs by SOC and PT.
 - Serious TEAEs that occurred after the first dose and before the second dose: All, study drug-related, and injection procedure-related TEAEs by SOC and PT. For subjects who did not receive the second dose, only serious TEAEs that occurred up to Day 57 (Day 1 being the day when the first dose was administered) will be included.
 - Serious TEAEs that occurred after the second dose in subjects who received the second dose: All, study drug-related, and injection procedure-related TEAEs by SOC and PT.
 - TEAEs with severity of 3/4/5/Severe/Life-Threatening/Fatal that occurred after the first dose and before the second dose: All, study drug-related, and injection procedure-related TEAEs by SOC and PT. For subjects who did not receive the second dose, only relevant TEAEs that occurred up to Day 57 (Day 1 being the day when the first dose was administered) will be included.
 - TEAEs with severity of 3/4/5/Severe/Life-Threatening/Fatal that occurred after the second dose in subjects who received the second dose: All, study drug-related, and injection procedure-related TEAEs by SOC and PT.
 - TEAEs that occurred within 2 days after either the first dose or the second dose (ie, post dose TEAE start date - dosing date \leq 2): All, study drug-related, and injection procedure-related TEAEs by SOC and PT.

- TEAEs that occurred within 2 days after the first dose: All, study drug-related, and injection procedure-related TEAEs by SOC and PT.
- TEAEs that occurred within 2 days after the second dose in subjects who received the second dose: All, study drug-related, and injection procedure-related TEAEs by SOC and PT.
- TEAEs that occurred within 7 days after either the first dose or the second dose (ie, post dose TEAE start date - dosing date ≤ 7): All, study drug-related, and injection procedure-related TEAEs by SOC and PT.
- TEAEs that occurred within 7 days after the first dose: All, study drug-related, and injection procedure-related TEAEs by SOC and PT.
- TEAEs that occurred within 7 days after the second dose in subjects who received the second dose: All, study drug-related, and injection procedure-related TEAEs by SOC and PT.
- Two event rate estimations adjusted by subject year of follow-up will be provided for all TEAEs by SOC and PT:
 - Total number of events divided by the total length of the TEAE period over all subjects in the SAF of each treatment group.
 - Total number of subjects with an event in question divided by the total length of the TEAE period. For a subject with event, the time from first dose to the first event will be counted towards the denominator. For a subject without event, the time from first dose to the end of the TEAE period will be counted towards the denominator.

The above TEAE summaries will present the number (n) and percentage (%) of subjects experiencing an TEAE by SOC and PT. Multiple occurrences of AEs of the same PT (or SOC) in the same subject will be counted only once for that PT (or SOC). For tables presenting severity of events, the worst severity will be chosen for subjects with multiple instances of the same event. Relatedness to study drug or injection procedure is according to investigator's opinion.

Primary SOCs will be sorted by decreasing frequency in the combined REGN2222 group. Within each primary SOC, PTs will be sorted by decreasing frequency in the combined REGN2222 group.

The description of TEAEs reported by $\geq 5\%$ of subjects in any treatment group will also be performed for demographic and baseline factors including: sex, chronological age (≤ 3 months, > 3 months), gestational age (≤ 31 weeks 6 days, ≥ 32 weeks 0 days and ≤ 35 weeks 6 days), and region.

Subject listings for deaths, all serious TEAEs, TEAEs leading to permanent treatment discontinuation, TEAEs with severity of 3/4/5/Severe/Life-Threatening/Fatal, and treatment-emergent AESIs will be provided.

5.8.2. Analysis of Adverse Events of Special Interest and Preferred Terms of Interest for Identification of Hypersensitivity

Treatment emergent AESIs and PTs of interest for identification of hypersensitivity (as defined in Section 4.7.2) will be presented by SOC and PT, or by PT alone. The summaries will be sorted by decreasing incidence of PT within each SOC in the combined REGN2222 group if presented by SOC and PT. In addition, the following analyses will be performed to further characterize the safety profile in each treatment group:

- TEAEs that are PTs under the HLT of injection site reaction will be summarized by:
 - Number (and percentage) of subjects who experienced 1 vs. >1 events of injection site reaction.
 - Number (and percentage) of subjects who experienced at least one event of injection site reaction by highest severity.
 - Descriptive statistics including number of subjects, mean, median, standard deviation, minimum, Q1, Q3, and maximum will be provided for the following measures:
 - Number of events divided by the number of study drug injections each subject received. Note each dose of study drug can be administered via more than 1 injections according to the total volume of study drug determined by the subject's body weight.
 - Mean duration of events. The duration of an event is defined as (AE stop date - AE start date +1). If an AE is ongoing at the end of the study, the last visit date will be used in lieu of AE stop date. Mean duration is calculated as the duration averaged over all events experienced by a subject.
 - Number of days following the most recent study drug injection to the first event of injection site reaction.
 - Number of events and number (and percentage) of subjects with events that occurred within 2 days after dosing by PT. For subjects who did not receive the second dose, only those events that occurred up to Day 57 (Day 1 being the day when the first dose was administered) will be included.
 - Number of events and number (and percentage) of subjects with events that occurred beyond 2 days after dosing by PT. Only subjects who received the second dose will be included in this analysis.

